#### **2.2.4.3 Clinical Data**

The safety, tolerability, PK, and clinical activity of AMG 340 are currently being evaluated in this ongoing phase 1, open-label, dose-escalation and expansion study of AMG 340 in subjects with mCRPC. As of the safety data cutoff date of 08 March 2022, a total of 24 subjects were enrolled in the study; 1 subject did not receive investigational product. In cohort 5, a single grade 3 CRS event was observed that triggered the implementation of a priming dose per protocol Section 6.2.1.2.

All 23 subjects who received at least 1 dose of investigational product had a treatment emergent adverse event (defined as events that occurred or worsened on or after the first dose of AMG 340 until 90 days after discontinuation of AMG 340 or until the subject started another anticancer therapy, whichever occurred earlier). The most frequently reported adverse events ( $\geq 20\%$  of subjects) were nausea (13 subjects, 56.5%), vomiting (12 subjects, 52.2%), CRS (9 subjects, 39.1%), diarrhea (8 subjects, 34.8%), hypocalcemia (8 subjects, 34.8%), hypomagnesemia (7 subjects, 30.4%), dysgeusia (6 subjects, 26.1%), and hypophosphatemia (5 subjects, 21.7%). Eight subjects (34.8%) had at least 1 grade  $\geq 3$  adverse events. Grade 3 adverse events include anemia (3 subjects, 13.0%), aspartate aminotransferase increased (2 subjects, 8.7%), and thrombocytopenia, alanine aminotransferase increased, neutrophil count decreased, cytokine release syndrome, brain abscess, failure to thrive, confusional state, hydronephrosis, and hypoxia (each 1 subject, 4.3%). One subject (4.3%) had a grade 4 adverse events of neutropenia and thrombocytopenia, and 1 subject (4.3%) had a fatal adverse event of hemorrhage (cerebral hemorrhage following a fall).

One subject (4.3%) had an adverse event leading to discontinuation of AMG 340 (grade 2 cerebrovascular accident). Eight subjects (34.8%) had serious adverse events, including cytokine release syndrome (2 subjects, 8.7%), aspartate aminotransferase increased (2 subjects, 8.7%), and alanine aminotransferase increased, thrombocytopenia, brain abscess, failure to thrive, cerebrovascular accident, hematuria, and hemorrhage (cerebral hemorrhage following a fall) (each 1 subject, 4.3%). One subject had DLT events of neutropenia and thrombocytopenia.

As of 15 February 2022, preliminary PK data for AMG 340 were available for 20 subjects with progressive mCRPC in Study 20210249. Briefly, within the evaluated target dose range (█ to █ mg Q3W), the serum AMG 340 exposures increased in an approximately dose-proportional manner with mean estimated terminal half-life ( $t_{1/2,z}$ ) ranging from 4.16 to 8.57 days after a single dose.

Refer to the IB for additional information on AMG 340.

#### **2.2.5 Non-Amgen Investigational Product Background: Imaging Products**

In some countries/regions, █

█ and  $^{18}\text{F}$ -Fluorodeoxyglucose ( $^{18}\text{F}$ -FDG) are investigational products administered as part of positron emission tomography (PET)/computed tomography (CT) imaging assessments in this study. PET/CT imaging will be performed only at a select subset of participating study centers.

$^{68}\text{Gallium}$  and  $^{18}\text{F}$ -FDG are used for in vitro radiolabeling of specific carrier molecules which have been specifically developed and are used for diagnostic imaging with PET.

█ and  $^{18}\text{F}$ -FDG PET/CT are investigational imaging modalities used with increased frequency in several clinical indications including staging of intermediate-to-high -risk prostate cancer patients or restaging in patients with biochemical recurrence, showing superiority to choline PET/CT due to their higher accuracy (Kurash et al, 2020). A study by Fendler et al (2019) established high detection rates, positive predictive value, inter-reader reproducibility, and safety of

█ PET for localization of biochemically recurrent prostate cancer in a prospective multicenter trial meeting the primary endpoint: █ PET demonstrated 84% to 92% positive predictive value at 75% overall detection rate.

Additional information will be included in the imaging manual.

#### **2.3 Benefit/Risk Assessment**

AMG 340 is a T-cell redirecting immunotherapy that exhibits robust preclinical efficacy in models of advanced mCRPC. The pharmacology, toxicology, and PK profiles of AMG 340 have been adequately characterized to support initiation of phase 1 FIH clinical trials in subjects with mCRPC at a starting dose of █ mg Q3W. Taken together, these data and high unmet medical need in the proposed patient population reflect an acceptable rationale and risk for treating adult subjects with advanced mCRPC with AMG 340 in the context of a clinical trial. Refer to the IB for details.

As a FIH phase 1 study, Study 20210249 (formerly TNB585.001) has inherent risks. Patient monitoring, both clinical and via laboratory studies, necessitates more visits to the hospital and more blood draws compared to treatment with approved therapies. As there is limited information about the safety profile of AMG 340, unanticipated toxicities may occur. T-cell engaging therapies can cause immune mediated side effects that may require hospitalization, and rarely, fatal outcomes have been reported. In some circumstances these risks may even be amplified. Specifically, the risks associated with increased monitoring have been heightened by the COVID-19 pandemic that began in 2019.

Both the AMG 340 molecule and Study 20210249 are designed to minimize risk to subjects. Only subjects that are not candidates for treatment regimens known to provide clinical benefit in mCRPC are eligible to enroll. These subjects have exhausted all proven therapies to treat their cancer, and therefore the risk of not receiving an experimental therapy for which they are eligible is high. As described in Section [2.2.4](#), AMG 340 incorporates a unique anti-CD3 moiety selected for reduced cytokine secretion. The molecule is therefore expected to show reduced CRS, the main toxicity observed with T-cell activating-therapies. Without compromising the need for heightened subject monitoring in a clinical trial, the 20210249 Schedule of Activities was designed to minimize subject visits and inpatient stay.

Taken together, the preclinical data and study design reflect an acceptable rationale and favorable risk-benefit ratio for treating adult subjects with advanced mCRPC with AMG 340 within the context of a clinical trial. Refer to the IB for detailed data supporting AMG 340 development for the treatment of RR mCRPC.

The above benefit risk assessment supports the conduct of this clinical trial. Reference should be made to the IB for further data on AMG 340.

### **2.3.1        Key Risks**

Based on the biological mechanism, non-clinical studies and clinical experience with AMG 340, CRS is designated as an adverse drug reaction (ADR). The key safety risks for AMG 340 are summarized in [Table 2-2](#).

**Table 2-2. Key Safety Risk for AMG 340**

Safety Risk	Description
Identified Risk	
Cytokine release syndrome (CRS)	Signs and symptoms may include (but not limited to) the following: 

• constitutional – fever, rigors, fatigue, malaise

• neurologic – confusion, headache, mental status changes, dysphasia, tremors, dysmetria, gait abnormalities, seizure (refer to immune-effector cell associated neurologic syndrome [ICANS] guidance in Section 6.2.1.6.1.1)

• respiratory – dyspnea, tachypnea, hypoxemia

• cardiovascular – tachycardia, hypotension

• gastrointestinal – nausea, vomiting, diarrhea

• hepatic – transaminitis, hyperbilirubinemia

• hematology – thrombocytopenia, bleeding, hypofibrinogenemia, elevated D-dimer

• skin – rash

Potential Safety Concerns	
Tumor lysis syndrome	Signs and symptoms may include hyperkalemia, hyperphosphatemia, hyperuricemia, hyperuricosuria, and hypocalcemia, potentially causing lethal cardiac arrhythmias, seizures, and/or renal failure.
Gastrointestinal toxicities	Signs and symptoms may include nausea, vomiting, diarrhea, abdominal pain, gastrointestinal inflammation and ulceration; mostly associated with CRS.
Neurological toxicities	Signs and symptoms include confusional state, headache, dizziness, encephalopathy, tremor, aphasia, and syncope; mostly associated with CRS.

Clinical signs and symptoms of CRS will be continually monitored throughout the duration of the study and at the time points indicated in Schedule of Activities (Section 1.3). Refer to Table 6-6, and Sections 6.1.5, 6.2.1.6.1.1, and 11.10 for specific recommendations regarding the mitigation and management of the risk.

Coronavirus disease 2019 (COVID-19) infection may theoretically increase the signs and symptoms of CRS. Refer to Section 5.2 and section below for additional guidance related to COVID-19.

The key safety risks are described further in the AMG 340 IB.

### **COVID-19 Assessment**

Amgen closely monitors the COVID-19 pandemic around the world. As part of this effort, Amgen performs a rigorous assessment, considering the study design, patient safety, public health risk, benefit-risk assessment, as well as the burden on country healthcare systems. Decisions are made on a study-by-study and country-by-country basis to minimize risk to patients and avoid undue burden on healthcare facilities.

Patients who display symptoms consistent with COVID-19 infections or who have tested positive for COVID-19 should contact the investigator to ensure appropriate care as well as documentation and management of study activities.

Amgen considers that it is important to continue the proposed development of AMG 340 in this study in order to advance potential therapy options for patients as rapidly as possible, while balancing this with appropriate measures to monitor and mitigate the potential impact of COVID-19.

Subjects enrolled in this study are permitted to receive vaccinations for COVID-19.

### **3. Objective(s) and Endpoint(s)**

Objectives	Endpoints
Primary	

Evaluate the safety and tolerability of AMG 340 when administered as monotherapy.

	

Treatment-emergent adverse events

Treatment-related adverse events

Changes in vital signs and clinical laboratory tests

Determine the maximum tolerated dose (MTD) or recommended phase 2 dose (RP2D) for AMG 340 when administered as monotherapy.

	

Dose-limiting toxicities (DLTs)

Evaluate the pharmacokinetics (PK) of AMG 340 when administered as monotherapy.

	

PK parameters of AMG 340 including, but not limited to:

<math>C_{max}</math>

Time to <math>C_{max}</math> (<math>T_{max}</math>)

Area under the concentration-time curve within a dosing interval (<math>AUC_{0-t}</math>)

Secondary	

Evaluate the clinical activity of AMG 340 when administered as monotherapy.

	

Objective response (OR) per RECIST 1.1

Overall survival (OS)

Progression-free survival (PFS) (radiographic and PSA)

6-month landmark radiographic PFS

PSA response (30%, 50%, 70% and 90%)

	

• Time to progression (radiographic and PSA)

• Duration of response (DOR) per RECIST 1.1

• PSA DOR based on PSA50

• Time to symptomatic skeletal events (SSE)

--	---

Exploratory	

• Evaluate immunogenicity of AMG 340

	

• Incidence of anti-AMG 340 antibody formation

#### **4. Study Design**

##### **4.1 Overall Design**

This is a phase 1 open-label, dose-escalation and expansion study evaluating the safety, PK, PD, and clinical activity of AMG 340 in subjects with progressive mCRPC who have received at least 2 or more prior lines of systemic therapy ('Line/regimen of therapy' is defined as a course of therapy [at least 1 cycle uninterrupted by progressive disease, cycle disruption due to toxicity or intolerance is acceptable]). To be eligible for enrollment in this study, subjects should have previously been exposed to, intolerant of, ineligible for, or declined therapy with both a novel anti-androgen (eg, abiraterone, enzalutamide) and a taxane (eg, docetaxel). Approximately 100 subjects will be enrolled at sites in the US.

The study will consist of 2 Parts: a monotherapy dose escalation (Part A; Section 4.1.1) and a monotherapy dose expansion (Part B, Sections 4.1.2). The overall study design is described by a study schema in Section 1.2. The endpoints are defined in Section 3.

Participants in this clinical investigation shall be referred to as “subjects”. For the sample size justification, see Section 9.2.

Study visits and evaluations will be performed at screening and at day 1 of each cycle. Based on a 3-week cycle, additional study visits and evaluations will be performed on days 2, 3, 8, and 15 during cycle 1, on day 15 only in cycles 2 and 3, and on days 2 and 15 in cycle 6. If a priming dose or multiple priming doses are implemented, additional visits and evaluations will occur during cycle 1.

Evaluations will include physical examination, hematology, and chemistry tests prior to all study drug dosing, at the End of Treatment (EOT) visit (within 30 days after the last dose of study drug), and safety follow-up (SFU) visit. PSA will be assessed at screening and on day 1 of every cycle. Computed tomography (CT), bone scintigraphy, FDG-PET and PSMA-PET (in subjects that sign optional consent, in Part B) will be assessed at screening and then on day 1 of every third cycle. Once reliable PK data are available for AMG 340, and if  $T_{1/2}$  exceeds 18 days, the 90-day post-last treatment visit may be performed at a time more remote from the last dose in order to capture PK data at  $T \geq 5 \times T_{1/2}$ . Adverse events, serious adverse events, concomitant medications, laboratory data, and vital signs will be assessed throughout the study.

Blood and tissue samples for evaluation of the PK and ADA (see Section 8.5 and Section 8.7, respectively) and PD (see Section 8.8) of AMG 340 will be collected at designated time points throughout the study.

#### **4.1.1            Part A: Monotherapy Dose Escalation**

Part A was initiated and employs a dose escalation design to evaluate the safety, tolerability, PK and PD profiles of single-agent AMG 340 administered Q3W. Up to 60 subjects with progressive mCRPC who have received at least 2 prior lines of therapy will be enrolled in Part A. Subjects should have previously been exposed to, intolerant of, ineligible for, or declined therapy with both a novel anti-androgen (eg, abiraterone, enzalutamide) and a taxane (eg, docetaxel). In Part A, cohorts have initially enrolled single subjects (Yuan et al, 2016). Proposed dose levels for AMG 340 are outlined in [REDACTED] but the number of dose levels tested will depend on safety, PK/PD, and activity data.

Upon the first occurrence of a grade  $\geq 2$  adverse event that is not unequivocally due to the subject’s underlying malignancy or other extraneous cause, the corresponding cohort, and all subsequent cohorts in Part A, will be enrolled according to a BON design

with the target toxicity rate of 30%. Cohorts will enroll a minimum of 3 subjects; up to 6 subjects may be enrolled concurrently (if transition from single subject cohorts to BOIN is triggered by a DLT, 6 subjects will be enrolled in that cohort). A maximum of 60 subjects will be enrolled in Part A. No more than 2 subjects should be dosed on the same day when enrolling new cohorts. Following the first assessment of BOIN dose escalation/de-escalation at a given dose level, additional subjects may be enrolled according to the BOIN criteria (Yuan et al, 2016).

If a response (partial response [PR] or complete response [CR]) is observed in a single subject cohort, cohorts enrolling thereafter will follow a BOIN design as above. The BOIN dose escalation and de-escalation boundaries ( $\lambda_e$  of 0.236 and a  $\lambda_d$  of 0.358) are shown in [Table 4-1](#).

**Table 4-1. Dose Escalation and De-escalation Boundaries**

Actions	Number of subjects treated at current dose cohort									
	1	2	3	4	5	6	7	8	9	10
Escalate if # of DLTs $\leq$	0	0	0	0	1	1	1	1	2	2
De-escalate if # of DLTs $\geq$	1	1	2	2	2	3	3	3	4	4

DLT = dose limiting toxicity

Source: Yuan et al, 2016

Dose escalation has been started as planned with a Q3W dosing schedule, which may be altered after cumulative review of safety and PK data and a protocol amendment. Administration of the first dose of AMG 340 to the first subject in each cohort must await completion of the first cycle (3 weeks) of the prior dose level, and a review of the safety data by the Dose Level Review Team (DLRT) (formerly referred to as the Safety Monitoring Group [SMG] – see Section 11.3). Input from biostatistical, PK and other

experts will be sought as necessary. Cohorts  $Na$  (where N represents a Cohort number), b, c, etc, may be conducted in parallel. Not all dose level cohorts may be enrolled based on emerging safety data.

Based on the DLRT's ongoing review of emerging safety, PK/PD and clinical activity data, cohorts receiving intermediate doses between those proposed above may be implemented. Furthermore, it may become necessary to switch to an alternative dosing regimen. If the dosing schedule is switched, no dose modification should result in a predicted steady state  $C_{max}$  or AUC greater than that identified for the immediately prior lower dose level.

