## **6.2 Dose Modification**

### **6.2.1 Dose-cohort Study Escalation/De-escalation and Stopping Rules**

#### **6.2.1.1 Dose Escalation and Selection of the MTD/RP2D Dose**

DLT criteria (see Section [6.2.1.4.1](#)) will be used to make decisions regarding dose escalation. Dose escalation decisions will be based on clinically significant toxicity, DLT events and clinical pharmacology findings, and will be made by the DLRT. A simple majority of the DLRT is required to proceed with dose escalation; for quorum requirements, see Section [11.3](#).

Dose escalation will be based on the BOPN escalation/de-escalation criteria described above (and as illustrated in Yuan et al, 2016; [Figure 1-2](#)), with a target toxicity rate of 30% ( $\lambda_e$  of 0.236 and a  $\lambda_d$  of 0.358). The MTD will be identified via isotonic regression of pooled escalation cohort data ([Table 4-1](#)), according to the BOPN method (Yuan et al, 2016). An expansion dose (eg, RP2D) may be selected by the DLRT prior to the identification of the MTD based on an assessment of available safety, PK/PD, and activity data; in this case the DLRT will also decide whether dose escalation in Part A should continue in parallel. Additional priming doses and intermediate dose levels may

be investigated based on emerging safety, PK, PD, and efficacy data to identify the minimum safe and biologically effective dose (MSBED) [REDACTED]

When the DLRT completes their safety review of cycle 1 for a Cohort N (where N represents a Cohort number), and if that dose is deemed safe (eg, the DLRT endorses further dose escalation or the dose for Cohort N is determined to be the RP2D), any subjects that remain on study at a lower dose of AMG 340 may subsequently be treated at the dose assigned to Cohort N (eg, when the DLRT review for Cohort 5 is complete and the decision to escalate to Cohort 6 has been made, any subjects still on study from Cohorts 1 to 4 may have their dose increased to the dose corresponding to Cohort 5). Subject eligibility for such an escalation must be approved by the Medical Monitor(s) and treating investigator and will be determined on a case-by-case basis. At a minimum, to be eligible subjects must have previously received at least 2 cycles of AMG 340 at their current dose without any drug related toxicities that led to a dose reduction.

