Dose level review meetings voting will occur as follows: there will be a total of 3 votes, 1 for the medical monitor, 1 for the GSO or delegate, and 1 for all of the site investigators or delegates combined. Regardless of how many site investigators there are, all of the site investigators combined will have a total of 1 vote decided by a majority of the investigators (defined as greater than or equal to 50%).

DLRM recommendations to escalate to the next planned subject group/cohort, or to an intermediate subject group/cohort, must be by unanimous vote. If the voting members of the DLRT are not able to reach a unanimous recommendation on whether to escalate to the next planned subject group/cohort or to an intermediate subject group/cohort, then this should be reflected in the DLRM Memo. Other recommendations, such as expanding a subject group/cohort or lowering a dose will be made by a majority vote.

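### The printed BOIN tables have no rule that closes an overly toxic dose level, so their counts allow a return to a level with 3 of 3 DLTs unless the DLRT declines

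*Protocol*

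**What the plan says.** Protocol 4.1.1 moves Part A from single-subject cohorts to a BOIN design "with the target toxicity rate of 30%. Cohorts will enroll a minimum of 3 subjects". The boundaries are λe = 0.236 and λd = 0.358. Protocol Table 4-1 turns them into counts for 1 to 10 subjects in two rows, "Escalate if # of DLTs" and "De-escalate if # of DLTs". SAP Table 3-1 repeats both rows unchanged. Neither table has a third row.

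On repeat use of a level, Protocol 4.1.1 says: "Following the first assessment of BOIN dose escalation/de-escalation at a given dose level, additional subjects may be enrolled according to the BOIN criteria".

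Two other controls bear on the point.

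- **DLRT review.** Each new cohort waits for the prior level to complete cycle 1 and for a DLRT review (Protocol 4.1.1). Protocol 6.2.1.1 adds: "Dose escalation decisions will be based on clinically significant toxicity, DLT events and clinical pharmacology findings, and will be made by the DLRT". That section asks for a simple majority to proceed with escalation. Appendix 3 (Section 11.3) says a recommendation to escalate "must be by unanimous vote".
- **Stopping rule.** Protocol 6.2.1.3 is headed as dose cohort stopping rules. For Part A its only numerical trigger is unacceptable toxicity in more than 33% of all Part A subjects taken together, which suspends accrual.

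**The concern.** De-escalation moves the next cohort down but does not close the level it leaves. If the lower level then looks safe, the escalate row points straight back up. A written rule that sends subjects back to a level where every earlier subject had a DLT exposes them to toxicity that the data already show to be very likely. In the short term it cannot even change the table's own decision. This is a first-in-human T-cell engager with CRS as an identified risk, and on the text shown the only dose-specific protection is committee discretion.

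**Working it through.** **Inputs.** The target rate of 30%, the two λ values and the 20 table entries come from Protocol 4.1.1 and Table 4-1. The base of 23 dosed subjects, one with DLTs, is from Protocol 2.2.4.3 (March 2022 cutoff). The Beta(0.6, 1.4) prior is from the siltuximab rule in Protocol 9.4.1.1. The uniform prior and the 0.95 cutoff are assumptions; the documents give neither for dose levels.

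**1. The plan's own table.** Take φ = 0.30 with the usual BOIN defaults φ1 = 0.6φ = 0.18 and φ2 = 1.4φ = 0.42 (assumed).

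- λe = ln[(1−φ1)/(1−φ)] / ln[φ(1−φ1)/(φ1(1−φ))] = 0.2365
- λd = ln[(1−φ)/(1−φ2)] / ln[φ2(1−φ)/(φ(1−φ2))] = 0.3585

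Rounding λe·n down and λd·n up gives 0,0,0,0,1,1,1,1,2,2 and 1,1,2,2,2,3,3,3,4,4. All 20 entries reproduce. What is printed is correct; the question is what is absent.

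**2. The return path.**

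- Level d shows 3/3. At n=3 the de-escalate count is ≥2, so go to d−1.
- Level d−1 shows 0/3. At n=3 the escalate count is ≤0, so go to d.
- If the true DLT rate at d−1 is q, then P(0/3) = (1−q)³, which is 0.86, 0.73, 0.51 and 0.34 for q = 5%, 10%, 20% and 30%.
- If d−1 already held 0/3, up to one DLT in the next three still gives ≤1/6, which is escalate. At q = 10% that has probability 0.729 + 3(0.1)(0.81) = 0.972.
- Three more subjects at d give between 3/6 and 6/6. The de-escalate count at n=6 is ≥3, so every outcome is de-escalate.
- If the true rate at d were 60%, those three subjects would have 3 × 0.6 = 1.8 expected DLTs.

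**3. Evidence at the point of return.** With a uniform prior the posterior after x DLTs in n is Beta(1+x, 1+n−x).

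| Data | P(DLT rate > 30%) |
|---|---|
| 3/3 | 1 − 0.3⁴ = 0.992 |
| 4/6 | 0.971 |
| 5/9 | 0.953 |

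With the plan's siltuximab prior Beta(0.6, 1.4), 3/3 gives 0.976. The trigger attached to that prior is 0.80.

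**4. The pooled rule.** From 1/23, adding 3/3 gives 4/26 = 15%; adding 0/3 one level down gives 4/29 = 14%. From that base, 11 consecutive subjects with toxicity are needed to exceed one third (12/34 = 35%; ten give exactly 11/33). These sums count every DLT as unacceptable toxicity, which the protocol does not say. Section 6.2.1.4 applies that word to toxicity persisting after two dose reductions.

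**5. What an elimination row would look like.** The smallest x with P(rate > 0.30) > 0.95 under the uniform prior is:

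| n | 3 | 4 | 5 | 6 | 7 | 8 | 9 | 10 |
|---|---|---|---|---|---|---|---|---|
| Eliminate if DLTs ≥ | 3 | 3 | 4 | 4 | 5 | 5 | 5 | 6 |

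**The case against.** **An elimination rule may exist where it cannot be seen.** The protocol applies BOIN as set out in a cited paper and in Figure 1-2. The figure is not shown in the text reviewed, and the paper is in neither document's reference list. This stands. The supportable statement is that no text shown closes a level, not that the trial has no such rule. A rule that governs exposure should still be printed in the tables that sites and the DLRT use.

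**The DLRT would not allow it.** Much of this stands too. Review precedes every new cohort, decisions rest on more than counts, levels may be skipped and intermediate doses inserted. A reader might infer that the plan requires re-entry to a level with 3/3. It does not; it permits it. But the safeguard is discretionary, and its voting rule is stated in two incompatible ways.

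**The pooled rule protects subjects.** It could early in a trial: 3/3 after three subjects without toxicity is 3/6 = 50%. It would not from the reported base, and it never acts on one level.

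**A sponsor may see this as rare.** It depends on the dose-toxicity curve. A worst-case simulation (cohorts of three, at most 30 subjects, no DLRT override) had a sharp jump to a true rate of 60% or 70% at the top level. Re-entry after the 0.95 bound was crossed occurred in about 44% to 73% of trials, with about 2 to 4.5 more subjects at that level than with an elimination row. The spread reflects the assumed cap on subjects per level, which the documents do not set. With gradual curves re-entry is much less common. A reader should not take the upper figures as the expected behaviour of this trial, which had one DLT subject among 23.

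**Conclusion.** The gap holds as a matter of what is printed. The boundaries are correctly calculated, but on the counts alone a level with 3/3 DLTs stays open, and the next three subjects there could not alter the de-escalate decision. The probability that such a level exceeds the 30% target is 0.976 to 0.992 under the two priors in the working, so the finding does not hang on the prior. How often it would matter is uncertain: it needs a steep rise in toxicity and a DLRT that follows the counts. The conclusion also assumes that neither Figure 1-2 nor the cited BOIN paper supplies an operative elimination rule. The documents do not support saying that subjects will be re-exposed, or that discretion is no safeguard. They do support saying that no dose-specific closing threshold is written where it would be applied.

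**What to change.** 1. The sponsor should confirm whether Figure 1-2 or the cited BOIN method contains an elimination rule that the trial follows.
2. Add an elimination row to Protocol Table 4-1 and SAP Table 3-1, and state the prior and cutoff behind it. The row in step 5 of the working is an illustration; the sponsor should choose and justify its own.
3. State whether elimination also closes all higher levels, and what follows if the lowest level is eliminated.
4. Reconcile the voting rules in Protocol 6.2.1.1 and Appendix 3.

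The drafting cost is one row in two tables and a sentence or two. The statistical cost is occasional loss of an acceptable level. At a true DLT rate of exactly 30%, the illustrative row is met with probability 0.3³ = 2.7% at n=3, P(X ≥ 4 of 6) = 7.0% at n=6 and P(X ≥ 5 of 9) = 9.9% at n=9. Each figure is for a single look at that sample size. A stricter cutoff lowers these figures and gives less protection: at 0.99 with a uniform prior, 3/3 is still eliminated but n=6 needs 5 DLTs, not 4.
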